5.1I.1. Overview. There are 4 groups of participants in this study: Veterans, their support persons (SPs), their providers, and mental health leadership.

Veterans and SPs

Intensive Coaching Phase. Prior to initiating treatment for randomized treatment cases, providers will deliver family-supported PE for up to 2 dyads (Veteran and his/her SP), with intensive coaching and feedback by the investigative team (Intensive Coaching Phase). A study investigator will review the audio recording of each session delivered that is unique to family-supported PE (Sessions 1-2b) and provide feedback for each session. Providers will also have access to participants self-reports for patient-centered feedback on their progress in the intervention.

Intensive Coaching participants are not randomized, so their data cannot be used for the RCT. Consequently, they will be assessed at fewer time points (i.e., only 3 administrations of weekly assessments) and procedures used to establish inclusion/exclusion criteria will rely on less burdensome processes (chart review and self-reports), consistent with how inclusion/exclusion would likely be evaluated if this intervention was delivered in routine clinical care (see below for greater detail). We aim to enroll up 96 participants for this phase (48 Veterans and 48 SPs among on up to 24 providers, due to potential provider attrition).

Randomized Controlled Trial (RCT) Phase. For the RCT phase, we will aim to enroll 225 Veterans and 225 of their SPs (with the goal of randomizing 156 dyads or 312 participants). Veterans can be of any age and combat era and either self-referred (e.g., individuals who reach out to study team members about participating after hearing about the study) or provider-referred (e.g., seeking evidence based psychotherapies through the PTSD Clinical Teams at the Minneapolis, Ann Arbor, and Atlanta VAs). They will be randomly assigned to either Prolonged Exposure (PE) for PTSD, as delivered within routine clinical care or family supported PE. Related to potential risk, we will not include Veterans' who are actively suicidal or homicidal with an intent and/or plan, who have experienced an episode of psychosis or mania in the past 3 months, who have had a severe substance use disorder in the past 3 months, or who report moderate relationship violence (by either Veteran or SP support, during the screening process).

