In most cases, we expect that provider referrals will come from patients actively seeking mental health care. When a provider or off-team staff member refers a Veteran to study staff without first asking them if they would like to be called regarding a research study, we will send them a study letter and brochure and wait 7 days prior to efforts to reach them. If, upon contact, the individual has not received their study letter, we will offer to contact the individual again at a later date and to re-mail the recruitment letter. When a provider or off-team staff member refers a Veteran who has expressed an interest in being called regarding a research study, study staff will call the Veteran as soon as possible to give them information about the study and for initial screening. This eliminates a delay in getting Veterans into care, and follows the current clinic mandates regarding minimum wait times for evidence based treatment for PTSD. When Veterans referred through providers are deemed ineligible, we will notify their referring provider and refer Veterans back to their mental health care provider.

We will make up to 3 calls a week for 3 weeks, unless the Veteran declines recruitment or requests an alternative schedule (e.g., if he/she asks us to call more often to try to catch them at a time when they aren't busy or are somewhere in private). We will leave up to one

message per week, unless the Veteran requests no voicemails or requests an alternative schedule. See Materials for an example voicemail script.

Step 3. Upon contact with the Veteran, with their permission, a trained interviewer will then discuss the study and complete an initial screening, including for the presence of an eligible SP (see Table 4), willingness to include a SP in at least one session of PE, and presence of moderate intimate partner violence (SF CTS-2), and presence of symptoms of PTSD on the PC-PTSD-5 (see inclusion/exclusion criteria for further detail). When the veteran's baseline surveys are received prior to their structured clinical interview for inclusions/exclusions (described below), we will also review their PCL-5 scores for the presence of symptoms of PTSD. Veterans with a PCL of 27 or lower will be screened out and will not be scheduled for structured clinical interviews.

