The study procedures (assessment data gathering, intervention, session recording) and study design (including the nature of treatment) will be fully described to the participant at the time of the initial contact (and again at the time that consent is documented). See script for initial screening call in Materials. For interested and eligible Veterans, we will begin recruitment efforts for their SPs and begin or schedule the informed consent meeting with the Veteran to complete enrollment.

5.2C. SP Recruitment: IC and RCT Phases

After receiving Veterans' permission to contact their nominated SPs, the recruitment procedures will be similar for SPs. They will be sent a letter, a brochure describing the study, informing them they will be contacted and how to decline study recruitment efforts. This initial mailing will also include an Information Sheet including all of the components of informed consent to be discussed by telephone. They will be contacted by telephone by a trained interviewer to discuss the study, their interest, and assess the presence of moderate relationship violence on the SF-CTS and screen for PTSD, using the same schedule of contacts used for Veterans, described above. If the SP is unable to speak in private to complete the SF CTS-2 and PTSD screen (see Materials for script), we will offer mailed administration and/or schedule a time to administer the brief measure in private by telephone.

5.2D. Provider recruitment.

When it is time to recruit providers for exit interviews (after completing their treatment cases), we will email them to remind them about the interview. Providers will be able to respond to the e-mail to either opt out of contact for the study or to schedule an interview date and time. If providers do not respond to the e-mail, they will receive a follow-up e-mail and three phone calls from the study team. If we do not reach or hear back from the provider after those contacts, we will assume they are not interested in participating in the interview.

5.2E. MH Leadership recruitment.

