3. Have a SP (intimate partner, family member, or friend) with contact at least 3 times a week	Self-report item	8. Severe substance use problem in past 3 months	SCID-5-CT ¹²
4. Will allow a SP to participate	Self-report item	9. Moderate relationship violence	IPSVS Adapted ¹⁰⁸
5. Willing to be seen via telehealth when in-person treatment options aren't available.		10. Veteran has underlying medical condition or a planned medical procedure likely to impair ability to engage in treatment.	
		11. SP screens positive for PTSD	PCL-5
		12. Veteran and/or SP fails to complete baseline survey	

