Criteria for items 3-4 will be assessed through single yes/no self-report items administered to Veterans during telephone screens or on self-reports (IC participants only). Given the emphasis on flexibility, item 4 will require the Veteran to agree to (a) allow a SP to complete study assessments, (b) bring a SP to Session 1, if randomized to family supported PE, and (c) discuss further SP attendance with his/her provider. Variability in SP attendance will be included as a covariate in analyses and examined as a predictor of adherence. Relationship violence will be assessed by telephone from both Veteran and SP-report (item 9), defined as one or more episodes of severe violence in the past year (e.g., kicked or beat up) on the IPSVS Adapted Scale¹⁰⁶. We will exclude Veteran participants if he/she has an underlying medical condition or a medical procedure (item 10) planned that would greatly impair their ability to participate in a weekly psychotherapy (i.e., a severe seizure disorder making weekly attendance difficult or a planned major surgery within a month of beginning treatment). This item will be assessed during the initial phone screening. We will administer a PTSD screen (PCL-, response options adapted to a yes/no format for efficiency of delivery by telephone) to SPs by telephone and exclude SPs who screen positive for PTSD on the PCL-5. SPs and Veterans will be required to complete a baseline survey assessment before they can be randomized to a study arm. Failure to complete the baseline survey will result in study ineligibility (item 11). If a family member is determined to be ineligible due to a positive PTSD screen or failure to complete his/her baseline survey, but the Veteran is otherwise eligible, the Veteran will be contacted by telephone and given the opportunity to designate another family member for participation. The details of the reason their initial SP was ineligible will not be disclosed.

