Regarding relationship violence, when the veteran reports they have been the target of moderate violence from their SP, the study team, under the supervision of the local Site PI, will determine if the violence should be the immediate focus of clinical attention. That is, (1) is the reporter is in danger of harm and, therefore, the focus of clinical attention should be on safety, or (2) would the reporter prefer to focus on IPV rather than PTSD. Importantly, each Site PI is a licensed, clinical psychologist with the appropriate training and expertise to make these

decisions. If the violence should be the focus of immediate clinical attention, then the dyad will be deemed ineligible and provided appropriate referrals. If the violence should not be the focus of clinical attention (e.g., the reporter is not in danger and does not wish to focus on IPV) the reporter may select a different loved one with which to participate in the study.

The new SP will also be screened and subject to the same inclusion/exclusion criteria, including that the new SP cannot be ineligible due to moderate IPV towards the veteran. The original SP will be deemed ineligible. The details of the reason the initial SP was ineligible will not be disclosed. The reporting dyad member(s) will be provided with resources and referrals for IPV (see IPV risk algorithm). Ineligible dyads may be re-evaluated for eligibility when this exclusionary criteria has been resolved (i.e., one year has passed without an episode of severe violence or six months without minor violence).

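### The relationship-violence exclusion is labelled moderate but defined as severe, and the rule for re-evaluating excluded dyads matches neither

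*Combined protocol and SAP*

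**What the plan says.** Section 5.3, Table 4, lists the exclusion as "9. Moderate relationship violence" and gives its measure as "IPSVS Adapted ¹⁰⁸". The text after the table takes up the same item by number, says that both dyad members are asked by telephone, and has the criterion "defined as one or more episodes of severe violence in the past year", measured on the IPSVS Adapted.

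Other sections use *moderate*. The overview in Section 5.1I.1 leaves out Veterans "who report moderate relationship violence (by either Veteran or SP support, during the screening process"). In Section 5.2B.2 the Veteran screening call covers "presence of moderate intimate partner violence (SF CTS-2"). In Section 5.2C the call to the support person (SP) is to "assess the presence of moderate relationship violence on the SF-CTS and screen for PTSD". The consent procedure in Section 5.4A makes the dyad ineligible when the SP reports moderate aggression.

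Two further rules sit at the end of Section 5.3. A Veteran who has been the target of moderate violence from the SP may, after a supervised site determination, take part with a different SP. An excluded dyad may be looked at again once the criterion is resolved, which is explained as "one year has passed without an episode of severe violence or six months without minor violence".

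Section 6.0 says that severe partner violence reported on the baseline survey is part of the exclusion criteria.

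**The concern.** The plan presents this exclusion as a protection against risk, and in one arm the SP joins treatment sessions. Such a criterion needs one severity level and one look-back period. Here the severity word changes between the label, the definition and the re-evaluation rule, and no section says which governs. Staff following the label and staff following the definition could reach opposite decisions on the same dyad. What is at stake is the reliability of the safety screen and a clear description of who was eligible.

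**Working it through.** The point involves no arithmetic beyond comparing time windows. The check sets every current statement of the criterion side by side and then classifies example dyads under each.

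| Place | Severity | Instrument | Other |
|---|---|---|---|
| 5.1I.1, RCT phase | moderate | not named | report by either member; no replacement SP route |
| 5.2B.2, Step 3 | moderate | SF CTS-2 | list ends with a pointer to the eligibility criteria |
| 5.2B.3, Steps 1 and 3 | moderate | SF CTS-2 | Intensive Coaching phase |
| 5.2C | moderate | SF-CTS | SP call, both phases |
| 5.3, Table 4, item 9 | moderate | IPSVS Adapted | cited to reference 108 |
| 5.3, text on item 9 | severe, one or more episodes, past year | IPSVS Adapted | cited to reference 106 |
| 5.3, Veteran as target | moderate | not named | replacement SP possible |
| 5.3, re-evaluation | severe (one year) or minor (six months) | not named | |
| 5.4A | moderate | not named | dyad ineligible; no replacement SP route |
| 6.0 | severe | baseline survey | |

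**Is moderate defined anywhere?** No section defines it or gives a cut-off. *Severe* does have content: Section 5.3 gives kicking and beating up as examples, and both acts are among the seven that Section 6.0 lists as severe.

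**Example dyads.**

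1. *A severe episode in the past year.* Excluded under the definition, and under the label if moderate is read as a minimum level.
2. *Moderate but not severe violence in the past year.* Excluded by the label in Table 4 and in Sections 5.1I.1, 5.2B.2, 5.2C and 5.4A. Not excluded by the definition in Section 5.3.
3. *Minor violence only, within six months.* Not excluded by the definition. No entry rule names minor violence, yet the re-evaluation rule treats it as something that must have ceased.
4. *A severe episode seven months ago and no minor violence for six months.* Excluded by the definition, since 7 months is less than 12. The second clause of the re-evaluation rule is met, and the two clauses are joined by *or*, so re-evaluation is open.

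**Can the re-evaluation rule be read to fit?** There are two readings. If either clause is enough, the six-month clause opens re-evaluation within the one-year look-back, as in example 4. If instead each clause applies to dyads excluded at that severity, the look-back conflict disappears, but minor violence then becomes a ground for exclusion that no entry rule states. Neither reading agrees with the definition.

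**Replacement SP.** Section 5.3 keeps open a route for a Veteran who was the target. Sections 5.1I.1 and 5.4A state the exclusion without mentioning it.

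**Instrument.** The recruitment sections name SF CTS-2 or SF-CTS; Section 5.3 names IPSVS Adapted. Reference 108, cited in Table 4, is a short form of the Revised Conflict Tactics Scales. Reference 106, cited in the text, is absent from the reference list, and Section 5.2B uses the same number for recruitment methods.

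**The case against.** The strongest reply is that Section 5.3 labels the criterion once and then defines it, so *moderate* is only a name for one or more severe episodes in the past year. Section 5.2B.2 points its reader to the eligibility criteria, and Section 6.0 agrees with the definition. This has weight: the sections that say moderate offer no rival cut-off. It does not settle the matter, because the closing paragraphs of Section 5.3 use moderate, severe and minor as separate words, and the re-evaluation rule disagrees with the definition whatever the label means.

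It is also fair that a re-evaluated dyad is not thereby admitted and would meet the one-year rule again. In that case the six-month clause does nothing for example 4, which is itself a reason to reconcile it.

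On the replacement SP, the violent pairing is never enrolled, and the new SP must pass the same screen. What remains is that two sections omit a permitted route.

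A reader might infer several stronger points that the documents do not support:

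- *Three entry thresholds.* Entry is stated at two levels. Minor violence appears only in the re-evaluation rule.
- *Undefined eligibility for every dyad with minor violence.* The definition does not exclude them, and no section does so at first screening.
- *Two different instruments.* Table 4 ties the IPSVS Adapted to a Conflict Tactics Scales short form, so the recruitment sections may simply carry a name that was not updated. The measures themselves are in study materials that the documents do not reproduce.
- *An adverse-event rate that depends on the cut-off.* For post-treatment and follow-up surveys, Section 6.0 sets its own reporting threshold by listing seven acts.
- *Sites already applying different rules.* Staff training, scripts and a risk algorithm are mentioned but not shown. Divergence is possible, not demonstrated.

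**Conclusion.** The inconsistency is real and should be corrected. The criterion is labelled moderate and defined as severe, moderate is never defined, and the re-evaluation rule matches neither. The dyads whose first-screening outcome turns on the section followed are those with moderate but not severe violence in the past year. This assumes that moderate is a level below severe, as the separate use of the words in Section 5.3 suggests. If the definition is taken as the whole meaning of moderate, entry has a single threshold under a misleading label, and the re-evaluation conflict remains.

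The documents give no frequencies by severity, so the number affected could be none or could be every dyad screened in that band. Section 5.4A settles eligibility before randomisation, so power and the comparison between arms are unaffected. The consequence is for the consistency of a safety screen and the description of the enrolled population.

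**What to change.** Reconcile Sections 5.1I.1, 5.2B.2, 5.2B.3, 5.2C, 5.3 (including Table 4) and 5.4A so that they share:

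- one severity definition and one look-back period;
- one instrument name, with a reference that is in the list;
- one rule on when a Veteran may name a replacement SP.

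Make the re-evaluation rule use the same severity and time window as the exclusion, and state how its clauses combine. Keep the sentence in Section 6.0 about baseline exclusion consistent with the result. Then check the screening scripts at the three sites against the agreed text. Which threshold applies is for the investigators and the IRB to decide; this review does not propose one.

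The cost is protocol wording and a script check. The sample size and the analysis do not change.

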5.4 Informed Consent Procedures

5.4A. SP Informed Consent.

We will seek an approval of verbal informed consent over the phone and waiver of written informed consent. All contact between study staff and SPs randomized to standard PE (without family involvement) will be remote (i.e., by mail and telephone). The study poses minimal risks, waiving informed consent does not affect the well-being of participants, and decreases participant burden that would be associated with scheduling and attending an in-person appointment at the VA hospital, especially for SPs who have full time jobs and have never been to the VA hospital. Verbal consent will be obtained by telephone, pending final confirmation of Veteran's eligibility at the eligibility assessment/consent described above.

During the initial phone call with SPs, all study procedures (assessment data gathering, intervention, audiotaping) will be fully described to the participant using the Information Sheet SPs received by mail to guide the discussion. Participants will be informed of the study design (including, for RCT participants, that they will be randomized to condition and will receive notice of their condition after the Veteran signs informed consent documents and Veteran eligibility is finalized) before they decide to participate. After reviewing the study and answering all questions, for those SPs who remain interested in participating, the consenting staff will ask to audio record their consent to the study and consent to audio recording treatment sessions (if assigned to family supported PE).

If Veterans are deemed ineligible due to inclusion/exclusion criteria or lack of interest, SPs will be informed that full inclusion/exclusion criteria were not met for the Veteran and thus the dyad is no longer eligible for enrollment. Specific details on which inclusion/exclusion criteria (including level of interest in the study) will not be disclosed. The same approach will be used for SPs' who decline participation or report moderate relationship aggression (i.e., Veterans will be informed that full inclusion/exclusion criteria were not met and thus the dyad is no longer eligible for enrollment). Appropriate alternative referrals to mental health treatment, including substance use treatment or psychotherapy, or to address relationship aggression will be made as upon request and when clinically indicated (i.e., positive screens for psychosis, substance use, suicidality, homicidally, etc.).

Of note, while consent takes place after the initial phone screening, randomization (RCT phase only) does not take place until participants have met inclusion/exclusion criteria. Since we are proposing that consent procedures for SPs be the same regardless of their treatment assignment (consent by phone), we do not need to know randomization when we are recruiting and consenting SPs. Once both members of the dyad have been deemed eligible for the study,

participants will be notified of their randomization when it is time to schedule their (or the Veteran's) first treatment session.

5.4B. Veteran Informed Consent.

After completing the recruitment steps described above, Veterans will participate in informed consent procedures. Veteran participants will participate in informed consent over the telephone with a study staff member. Subjects can meet with a study staff member for in-person informed consent if they prefer. In this case, participants meeting face-to-face for informed consent will be required to sign an official informed consent form instead of having their consent recorded.

Informed consent will be obtained before obtaining any Baseline self-reports (IC and RCT) or Baseline interviews (RCT and up to 10 IC cases). As these Baseline procedures are also necessary for establishing final eligibility (RCT: SCID-5-CT and CAPS-5; IC: PCL-5, PHQ-9, AUDIT, DAST), Veterans will be notified that the baseline procedures are necessary for establishing final eligibility and they may be deemed ineligible for the study after these procedures. For IC participants, those who meet final inclusion/exclusion criteria and remain interested will proceed with treatment (family-supported PE). For RCT participants, those who meet final inclusion/exclusion criteria and remain interested will then be randomly assigned. They will receive notification of their assignment when contacted to schedule their first therapy appointment. Individuals deemed ineligible will be told by telephone and Veterans referred back to their referring providers.

When Veterans are deemed ineligible by a study assessor after completion of the Structured Clinical Interview (i.e., positive screens for psychosis, substance use, suicidality, homicidality, etc.), study staff will communicate the assessment results of these ineligible subjects back to the treatment team (non-study clinical staff) for purposes of patient treatment planning and continuity of care. Conveying a patient's assessment results to the treatment team allows patients to be referred to appropriate treatment in a timely manner, while also eliminating any inconvenient and redundant reassessments. This will be proposed to participants during informed consent, and patients will have the ability to decline this request.

The site PI at each location will be responsible for training and supervising others at their site in obtaining informed consent. All staff will have completed all necessary human subjects trainings (e.g., TMS trainings and CITI training). Those obtaining informed consent will emphasize to the individuals that participation in the study is voluntary and that they can choose not to participate in any part of the study at any time.

Veteran participants will receive all of the information contained within informed consent by mail. The mailing will contain an opt-out option for those who do not want to be contacted any further along with 1) information explaining the risks and benefits of study participation, 2) their rights as study participants and their privacy rights and 3) required elements of informed consent. This material will then be reviewed by telephone prior to participation and verbal informed consent will be obtained and recorded. When the telephone consent is obtained, they will have already had the opportunity to review study details, consider their participation, and consult with loved ones about participation. Discussing this material with a staff member over the phone will provide greater time and freedom to consider or decline study participation, prior to investing more time and energy in the study. Participants will also verbally consent to permitting the use of audio/video recordings throughout the study. All consent will be recorded and saved in study files. Staff will solicit and answer all questions, and they will also ask the participants questions to ensure participant comprehension of the informed consent document including, but not limited to, what their understanding is of the risks and benefits of participation, when

assessments will occur and what topics they will cover. The team is sensitive to the importance of the informed consent process and will make every effort to ensure that participants give their consent voluntarily and fully informed about the potential risks and benefits.

If a participant requests to have an informed consent meeting face-to-face with a study staff member, this will be permitted. Some participants may prefer to coincide other appointments at the VA with an in-person consent meeting with our study staff. In this case, participants meeting in-person for informed consent will be required to sign an official informed consent form, a Consent for Production and use of Verbal or Written Statement, Photos, Digital Images, and/or Video or Audio Recordings by VA form, and an Authorization for Use and Release of Individually Identifiable Health Information form instead of having their consent recorded.

5.4C. Retaking Baseline Assessments

For safety and risk implications, we will require Veteran and SP participants to retake the baseline survey and preclinical assessment if the therapy start date would occur 2 months after their baseline data was collected. Time gaps between baseline data and therapy start dates can occur for various reasons, including scheduling issues, provider availability, patient travel arrangements, etc. It is important that patient baseline data is as close to therapy start dates as possible, as clinical data can change over several weeks. For example, in the gap between assessment and therapy start, patients could have a serious substance use relapse or a suicide attempt that would then make it clinically inappropriate for them to begin a trauma-focused therapy, prior to addressing their more pressing concerns around establishing their safety or sobriety. Additionally, we expect many of the constructs we assess to naturally change with time (e.g., family functioning, relationship satisfaction). So, baseline assessments that are more than 2 months old at the time of therapy start may no longer truly represent the patient, support person, or family functioning at the beginning of treatment, confounding study results.

Subjects will be informed of this requirement during the informed consent process and on the information packet or informed consent form. Participants would get paid again for retaking these assessments (\$40 for the baseline survey; \$50 for the preclinical interview).

5.4D. Receiving Baseline Surveys Before Subject Informed Consent

If a participant completes their survey before consent, this will not be immediately reportable to CIRB. Instead, staff will document this occurrence in a spreadsheet to be given to CIRB at continuing review. Staff will then be required to get consent from the participant within 30 days of receiving the baseline survey. If consent is not obtained within the 30 day window, the deviation is immediately reportable to CIRB and staff will complete a protocol deviation.

5.4E. Incentives.

IC phase: Participants will receive a \$25 incentive for Baseline self-reports, \$40 optional for baseline Cognitive Interviews, \$50 for optional Baseline Structured Clinical Interviews (Veterans only), \$5 per Weekly form, \$25 for Posttreatment self-reports, \$40 for optional posttreatment Cognitive Interviews, and \$50 for optional Posttreatment Structured Clinical interviews (Veterans only). Veterans can earn up to \$250 and \$170 for SPs. Telephone administration will be offered for interviews to increase response rates.

RCT Phase: Participants will receive a \$40 incentive for Baseline self-reports, \$50 for Baseline interviews (Veterans only), \$50 for Posttreatment self-reports, \$60 for Posttreatment interviews (Veterans only), and \$60 for 3-month follow-up self-reports. Veterans and SPs will be given weekly surveys during weeks 2, 4, 5, 6, 8, 10 and 12 of treatment. Participants will be

compensated \$10 for completing surveys during weeks 4, 5, 6, 10 and 12. The weekly surveys during week 2 and 8 will be lengthier and more thorough, thus participants will be paid \$20 for completing weekly surveys on those two weeks of treatment. Veterans can earn up to \$290 and SPs' \$190. Telephone administration will be offered for to increase response rates.

Up to 40 Veterans randomized to Partner Enhanced PE will be offered the opportunity to complete an over-the-phone qualitative interview. Veterans who are offered and complete the qualitative interview will be compensated \$60. The incentive for the qualitative interviews will not be reflected in the total amount a Veteran can receive, because it will not be offered to all participants.

5.4F. Communicating with Participants using MyHealtheVet Secure Messaging.

We will incorporate the use of MyHealtheVet application as a study communication method with participants. My HealtheVet is an online portal created by the Department of Veterans Affairs to help Veterans in managing their health care, work with healthcare providers to reach informed decisions, and improve their overall health. My HealtheVet offers a suite of tools including access to their health records and a Secure Messaging system to communicate with their healthcare team and other VA staff. Our study will use MyHealtheVet in study communication techniques so Veteran participants who use the application can access their health records, receive email reminders about appointments, and communicate with members of the study team using Secure Messaging.

5.4G. Provider and Leadership Informed Consent.

5.4G.1. Providers. Exit interviews with providers will take place by telephone. We will request a waiver of written consent from the IRB. We will obtain oral informed consent and consent to be audio-taped, both of which will be captured on the audio-recording. Once a provider schedules an interview, an Information Sheet, covering all the elements of informed consent, will be e-mailed. At the beginning of the phone interview, we will thoroughly describe the risks and benefits and give the potential participants time to ask questions. We will take extra care to ensure that they understand that their participation is voluntary and will not affect their employment.

Providers will be allowed to ask questions prior to the interviewer beginning the audio-recording. Once the provider indicates his/her willingness to agree to the elements of informed consent and audio-recording, the interviewer will turn on the recording device and confirm the participant's consent to both the interview and the audio recording. As participants received the information sheet reviewing all the elements of informed consent document by email, they will have ample time to review the consent document. Staff will solicit and answer all questions, and they will also ask the participants questions to ensure participant comprehension of the informed consent document including, but not limited to, what their understanding is of the risks and benefits of participation and what is being asked of them.

5.4H.2. MH Leadership. We will request a waiver of written consent from the IRB. Once a member of leadership schedules an interview, a copy of the Information Sheet will be e-mailed. At the beginning of the phone interview, we will obtain oral informed consent and consent to be audio-taped. MH leadership will be allowed to ask questions prior to the interviewer starting the audio-recording. Once the provider indicates his/her willingness to agree to the elements of informed consent and audio-recording, the interviewer will turn on the recording device and confirm the participant's consent to both the interview and the audio recording.

